## **7.6 12 Month Visit**

During the 12 month visit (365 days after surgery  $\pm$  8 weeks, study days 309 – 421), SF-12, VAS (back and leg), ODI and patient satisfaction will be collected; neurological status (reflex, sensory, motor); subject's current pain medication, work status, and smoking status will be

CONFIDENTIAL

This material is the property of Stryker Spine. Do not disclose or use except as authorized in writing by Stryker.  
Page 21

assessed. AP/Lateral and Flexion/Extension radiographs, and long standing lateral will be taken. CT scan to assess bony fusion, will be taken as well.

## 7.7 24 Month Visit

During the 24 month visit 24 months (730 days after surgery  $\pm$  8 weeks, study days 674 – 786), SF-12, VAS (back and leg), ODI and patient satisfaction will be collected; neurological status (reflex, sensory, motor); subject's current pain medication, work status, and smoking status will be assessed. AP/Lateral and Flexion/Extension radiographs will be taken. For subjects that did not have a successful fusion at Month 12, a 24 month CT scan will be taken to re-assess fusion.

# 8 Adverse Events

## 8.1 Reporting of Adverse Events

### 8.1.1 General Physical Examination Findings

At screening for inclusion into the study, any clinically significant abnormality should be recorded as a preexisting condition and reported on the History and Physical CRF. From the time of consent forward, any new clinically significant findings or abnormalities that meet the definition of a protocol defined AE must also be recorded and documented as an AE. AEs which are reportable under this protocol include those that related to the device, the index procedure, the lumbar spine and those that meet the definition of serious.

### 8.1.2 Adverse Event Reporting Period

The study period during which AEs must be reported is normally defined as the period from the initiation of any study procedures to the end of the study treatment follow-up. The start of study procedures is considered to be the point of consent. Any AEs which fit the protocol defined reportable events must be reported from the time of consent until study completion.

At each contact with the subject the investigator must seek information on AEs by specific questioning and, as appropriate, by examination. Information on protocol defined AEs should be recorded immediately in the source document and also in the appropriate AE module of the CRF. All clearly related signs, symptoms and abnormal diagnostic procedure results should be recorded in the source document and grouped under one diagnosis, as appropriate. The clinical course of each event should be followed until resolution or until it is determined at the end of the study that the AE will not resolve.

CONFIDENTIAL

This material is the property of Stryker Spine. Do not disclose or use except as authorized in writing by Stryker.  
Page 22

## 8.2 Adverse Event Definitions

Following is a list of general AE definitions.

### **Adverse Event**

An **AE** is any untoward medical occurrence in a clinical investigation subject, which changes the medical baseline of the subject. An AE can be an unfavorable and unintended sign, symptom or disease, whether or not related to the study device (AEs may also be referred to as complications). See Section 8.1, Reporting of Adverse Events, for the AE reporting requirements for this study.

### **Anticipated Adverse Event**

An **anticipated AE** is an AE, of which the nature, severity or degree of incidence is known and identified in applicable product labeling, published literature or the study protocol. The list of anticipated events is provided in Section 12, Risk/Benefit Assessment.

### **Serious Adverse Event**

A **SAE** meets one or more of the following definitions:

- Resulted in in-patient hospitalization
- Resulted in prolonged existing hospitalization
- Resulted in persistent or significant disability/incapacity
- Resulted in permanent impairment of a body function or permanent damage to a body structure
- Necessitated medical or surgical intervention to preclude permanent impairment of a body function or permanent damage to a body structure
- Was a life-threatening situation
- Resulted in patient death

### **Adverse Device Effect**

An **adverse device effect** (ADE) is a negative change in the subject's health that may have been caused by, or associated with, the use of the device.

### **Unanticipated Adverse Device Effect**

An **unanticipated adverse device effect** (UADE) is any serious adverse effect on health, safety or any life-threatening problem or death caused by, or associated with, a device if that effect is a problem or death not previously identified in nature, severity or degree of incidence, or any other unanticipated serious problem associated with a device and related to the rights, safety or welfare of subjects.

## 8.3 Adverse Event Notification to Study Sponsor

### 8.3.1 Notification to Ethics Committee/Institutional Review Board by Investigator

CONFIDENTIAL

This material is the property of Stryker Spine. Do not disclose or use except as authorized in writing by Stryker.  
Page 23

Reports of AEs (including follow-up information) must be submitted to the IRB according to their specific requirements. Copies of each report and documentation of IRB notification and receipt will be kept with the investigator's study files.

## 8.4 Recording of Adverse Events

All protocol defined AEs occurring during the study period must be recorded; this includes events that occur between scheduled visits. The clinical course of each event should be followed until resolution or stabilization.

## 8.5 Surgical Interventions

Surgical interventions are classified separately from adverse events. All surgical interventions (defined below) must be recorded on the appropriate eCRF within five (5) business days and reported to Stryker Spine within forty-eight (48) hours.

Surgical interventions are defined as follows.

Revision - a procedure that adjusts or in any way modifies or removes **part** of the original implant configuration, with or without replacement of a component of the original configuration. This may include adjusting the position of the original configuration.

Removal - a procedure in which *all* of the original implant components are removed, with or without replacement.

Supplemental Fixation - a procedure in which additional instrumentation that is not part of the original configuration under study is implanted (e.g., supplemental placement of a rod/screw system or a plate/screw system).

Reoperation - any surgical procedure at the treated level that does not remove, modify, or add any components to the implant configuration (e.g., repair of dural leak). Reoperations unrelated to the spinal implants (e.g., treatment for wound infection, or surgical decompression for pre-existing leg (radicular) pain) are recorded as surgical interventions, but are not considered individual subject failures.

Any device removed during the course of the study is required to be returned to Stryker Spine for analysis.

## 8.6 Medical Monitoring

CONFIDENTIAL

This material is the property of Stryker Spine. Do not disclose or use except as authorized in writing by Stryker.  
Page 24

It is the responsibility of the investigator to oversee the safety of the study at his/her center. This safety monitoring will include careful assessment and appropriate reporting of AEs, as previously noted. Stryker will conduct formal investigations via the Product Surveillance Department of those AEs which are submitted through our Product Inquiry System.

## 9 Statistical Plan

### 9.1 Efficacy Parameters

#### 9.1.1 Primary Objective Parameters

The primary objective parameters of this study are the change in pre-operative to post-operative radiographic outcomes of a cohort treated for degenerative disease at one or two levels implanted with the AccuLIF spinal system at one level via TLIF procedure with supplemental fixation. The primary objective will be evaluated at 12 months post-operatively.

Primary Radiographic parameters are defined as:

- Disc height (anterior, middle, posterior in millimeters)
- Foraminal height (in millimeters)
- Segmental lordosis (at each TLIF level in degrees)
- Regional Lordosis: (inferior endplate T12-S1 in degrees)
- Sagittal balance: (C7-S1 in millimeters)

  

- Success is defined as an increase of 3 degrees or more of segmental lordosis 12 months post operatively.

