#### 9.1.2 Primary Objective Hypothesis

Success is defined as an increase of 3 degrees or more of segmental lordosis post operatively. The primary null hypothesis is as follows:

H0: Subjects implanted with the AccuLIF spinal system will have less than 3 degrees increase in segmental lordosis 12 months post-operatively.

H0: Subjects implanted with the AccuLIF spinal system will have an increase of at least 3 degrees in segmental lordosis 12 months post-operatively.

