#### 9.1.3 Primary Objective Analysis

CONFIDENTIAL

This material is the property of Stryker Spine. Do not disclose or use except as authorized in writing by Stryker.  
Page 25

For the primary endpoint of an increase of 3 degrees or more of segmental lordosis, a one-sided analysis (alpha=0.05) will be used to assess significance. A one-sample t-test will be employed. Although the primary analysis will be at 12 months, similar analyses will be performed at each visit. Both the change from baseline and the results at each visit will be summarized.

For all other radiographic parameters, the change from baseline will be analyzed at each visit using two-sided, one-sample t-tests (alpha=0.05) comparing the change from baseline to 0.

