## 9.4 Statistical Methodology

### 9.4.1 Data Summary

All continuous data will be summarized using continuous descriptive statistics: number of subjects with responses (n), mean, standard deviation, median, minimum, and maximum. Changes from baseline, where appropriate, will be calculated as the follow-up measure minus the baseline measure, where baseline is defined as the last measure prior to the AccuLIF spinal system surgical procedure.

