### 9.4.2 Sample Size Calculation

CONFIDENTIAL

This material is the property of Stryker Spine. Do not disclose or use except as authorized in writing by Stryker.  
Page 27

Sample size calculations are based on the primary analysis of the change from baseline in segmental lordosis at 12 months, utilizing a one-sided, one-sample t-test. Based on previous experience it is assumed that the true change in segmental lordosis after 12 months will be 5 degrees. It is also determined that a change of at least 3 degrees is considered clinically meaningful. With a standard deviation of up to 6 degrees and assuming 90% power, 79 subjects are required to show a difference of at least 3 degrees. Assuming a dropout rate of up 20%, 100 subjects will be enrolled.

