#### **9.5 Efficacy Patient Population**

All patients enrolled in the study with any follow-up efficacy assessment (radiographic assessment) will be included in the efficacy patient population.

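### Does the primary t-test need a written rule for subjects who have two TLIF levels?

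*Combined protocol and SAP*

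**What the plan says.** **The measure is per level.** Section 9.1.1 lists "Segmental lordosis (at each TLIF level in degrees") among the primary radiographic parameters. The synopsis and section 2.1 say the same.

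**Two-level subjects can enter.** Section 4.1 admits subjects who need fusion at one or two adjoining levels. Section 4.2 excludes TLIF only when more than two levels need it.

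**The number of implanted levels is worded inconsistently.** Section 9.1.1 describes a cohort "treated for degenerative disease at one or two levels implanted with the AccuLIF spinal system at one level via TLIF procedure", and section 2.1 has the same phrase. The synopsis objectives instead describe the cage being implanted at one or two levels.

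**The analysis counts people.**
- The null hypothesis in 9.1.2 is "Subjects implanted with the AccuLIF spinal system will have less than 3 degrees increase in segmental lordosis 12 months post-operatively".
- Section 9.1.3 states "A one-sample t-test will be employed", one-sided at 0.05.
- Section 9.4.1 summarises continuous data by the "number of subjects with responses (n").
- Section 9.4.2 concludes that "79 subjects are required to show a difference of at least 3 degrees".
- Section 9.5 opens with "All patients enrolled in the study with any follow-up efficacy assessment (radiographic assessment) will be included in the efficacy patient population".

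No section supplied says how two level values become one. Section 9.1.6 mentions a formal statistical analysis plan, but only as the place where literature sources will be named. That plan and the appendices were not supplied.

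**The concern.** A one-sample t-test assumes independent observations. Two discs in the same patient share a surgeon, an operation and a spine, so their changes in lordosis are likely to be correlated. If both were entered as separate records, the standard error would be too small and the test against 3 degrees would reject too often.

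Even with the subject as the unit, a two-level subject could be represented by the mean, by one chosen level, or by the lower or higher level. These are different quantities. The choice determines what the 3-degree threshold and the standard deviation in 9.4.2 ("With a standard deviation of up to 6 degrees and assuming 90% power") refer to. The study is open and single-arm with one primary threshold test, so a reader may worry that an unwritten choice could be made after the values are seen.

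**Working it through.** **Inputs from the documents (9.1.3, 9.4.2).** One-sided alpha 0.05, true change 5 degrees, null value 3 degrees (difference 5 − 3 = 2), SD 6 degrees, power 90%, 79 evaluable and 100 enrolled, dropout 20%.

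**Inputs assumed, because the documents do not give them.** The number of two-level subjects among the 79, n2 = 4, 16 or 40 (about 5%, 20% and 50%), and the within-subject correlation between levels, r = 0.3 or 0.7. Unless stated otherwise, SD 6 is taken to apply to each level.

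**1. The plan's own figure.** With one value per subject, power comes from the noncentral t distribution with noncentrality 2·√n/6. It is 0.8985 at n = 78 and 0.9018 at n = 79, so 79 is the smallest adequate number. Allowing for dropout, 79/0.8 = 98.75, which rounds up to 99; the plan enrols 100. Both figures reproduce with the subject as the unit.

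**2. One value per subject, mean over levels.** The average variance relative to 6² is [(79 − n2) + n2·(1 + r)/2]/79.

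| n2 | r | Variance ratio | Effective SD | Power at 79 |
|---|---|---|---|---|
| 16 | 0.3 | (63 + 10.4)/79 = 0.929 | 5.78 | 0.92 |
| 16 | 0.7 | (63 + 13.6)/79 = 0.970 | 5.91 | 0.91 |
| 40 | 0.3 | (39 + 26)/79 = 0.823 | 5.44 | 0.94 |
| 40 | 0.7 | (39 + 34)/79 = 0.924 | 5.77 | 0.92 |

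Simulated type I error for this rule is 4.9% to 5.1%. If SD 6 already describes the per-subject mean, power is 0.902.

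**3. One value per subject, one level chosen in advance.** Mean and SD are unchanged, so power stays at about 0.90 (simulation 0.898 to 0.903).

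**4. Levels entered as separate records.** The true variance of the mean exceeds the assumed one by 1 + 2·n2·r/(79 + n2). The approximate type I error is 1 − Φ(1.645/√inflation).

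| n2 | r | Inflation | Type I error, formula | Type I error, simulation |
|---|---|---|---|---|
| 4 | 0.3 | 1.029 | 5.2% | 5.3% |
| 4 | 0.7 | 1.067 | 5.6% | 5.6% |
| 16 | 0.3 | 1.101 | 5.9% | 5.9% |
| 16 | 0.7 | 1.236 | 7.0% | 7.0% |
| 40 | 0.3 | 1.202 | 6.7% | 6.8% |
| 40 | 0.7 | 1.471 | 8.8% | 8.8% |

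The excess disappears if r = 0 or no subject has two levels.

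**5. The lower of two levels.** On average this lies 6·√((1 − r)/π) below the level mean: 2.83 degrees at r = 0.3 and 1.85 at r = 0.7. With 40 two-level subjects and r = 0.3, the mean of the analysed variable is 5 − (40/79)·2.83 = 3.57 degrees. Simulated power falls to between 0.21 and 0.77 over n2 = 16 to 40. The loss arises because the analysed variable no longer has the 5-degree true change that 9.4.2 assumes. It is not evidence that 79 is too few for the planned test.

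**The case for a change.** The strongest case for acting is that the choice can decide the result. With about 30% two-level subjects, correlation 0.5 and a true gain of exactly 3 degrees at every level, using the higher level rejects about 28% of the time and using the sum about 26%. Using the lower level rejects about 0.4% of the time. In an open single-arm study, a sentence fixing the rule costs almost nothing. The phrase placing the implant at one level does not settle the matter, because the same sections speak of each TLIF level and the synopsis allows two.

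The arithmetic stands, and so does the observation that no rule is written down. The inference to a flaw is weaker. The higher, lower and sum rules each test something other than a typical change of 3 degrees, and no section suggests any of them. Separate records would go against the subject counts in 9.1.2, 9.4.1, 9.4.2 and 9.5. The two rules that an analyst would ordinarily use agree on validity and give adequate power.

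The conflict between the synopsis and sections 2.1 and 9.1.1 on implanted levels is real, but it reads as a drafting slip. If only one level is implanted, the question does not arise. If two can be, one value per subject still gives a sound test.

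**Conclusion.** No change to the plan follows. The gap is a missing detail, and the surrounding text points to the sensible way of filling it. With the subject as the unit and either a level mean or one pre-chosen level, one-sided type I error stays near 5% and power at 79 subjects is 0.90 to 0.94. The sample size of 79 and the enrolment of 100 stand.

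The figures that look alarming belong to readings the plan does not favour: 5.3% to 8.8% type I error with separate records, and 0.21 to 0.77 power with the lower level. All the multi-level figures rest on an assumed two-level share (5% to 50% for the error rate, 20% to 50% for power), an assumed correlation of 0.3 to 0.7 and SD 6 at each level. The stated basis, one value per subject with SD 6, gives 0.902 without the assumed share or correlation. A rule may also exist in the separate analysis plan or the appendices, which were not available.

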#### 9.1.2 Primary Objective Hypothesis

Success is defined as an increase of 3 degrees or more of segmental lordosis post operatively. The primary null hypothesis is as follows:

H0: Subjects implanted with the AccuLIF spinal system will have less than 3 degrees increase in segmental lordosis 12 months post-operatively.

H0: Subjects implanted with the AccuLIF spinal system will have an increase of at least 3 degrees in segmental lordosis 12 months post-operatively.

#### 9.1.3 Primary Objective Analysis

CONFIDENTIAL

This material is the property of Stryker Spine. Do not disclose or use except as authorized in writing by Stryker.  
Page 25

For the primary endpoint of an increase of 3 degrees or more of segmental lordosis, a one-sided analysis (alpha=0.05) will be used to assess significance. A one-sample t-test will be employed. Although the primary analysis will be at 12 months, similar analyses will be performed at each visit. Both the change from baseline and the results at each visit will be summarized.

For all other radiographic parameters, the change from baseline will be analyzed at each visit using two-sided, one-sample t-tests (alpha=0.05) comparing the change from baseline to 0.

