## Study Synopsis

Title	A Prospective Multi-Center Evaluation of a hydraulic expandable TLIF cage for the treatment of Degenerative Disc Disease of the Lumbar Spine
Short Title	APROPOS (AccuLIF® Prospective Patient Outcomes Study)
Protocol Number	2015-L-001
Phase	Post-Market
Methodology	This is a prospective, post-market, multi-center, clinical evaluation of the AccuLIF expandable TLIF cage in patients requiring arthrodesis for degenerative disc disease (DDD) or DDD with up to Grade I spondylolisthesis or retrolisthesis at one or two contiguous levels between L2 and S1. DDD is defined as back pain of discogenic origin with degeneration of the disc confirmed by history and radiographic studies.
Study Duration	Enrollment period: approximately 9 months Study follow-up period: each subject will be followed for 24 months (2 years) Total study duration: approximately 36 months
Study Center(s)	Up to 10 centers in the US will participate
Hypothesis	
It is hypothesized that patients implanted with the AccuLIF expandable TLIF cage will show restoration of anterior, middle, and posterior disc height, improve segmental lordosis and maintain regional and global sagittal balance post operatively.
 
Primary success is defined as an increase of 3 degrees or more of segmental lordosis post operatively.
 
It is also hypothesized that patients implanted with the AccuLIF expandable TLIF cage will show improvement in post-operative clinical outcomes when compared to pre-operative clinical status.

CONFIDENTIAL

This material is the property of Stryker Spine. Do not disclose or use except as authorized in writing by Stryker.  
Page 7

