This material is the property of Stryker Spine. Do not disclose or use except as authorized in writing by Stryker.  
Page 11

Ancillary Devices	
The AccuLIF system is indicated for use with autogenous bone and/or allograft (cancellous or corticocancellous allograft chips) and supplemental fixation. Stryker supplementation fixation (Xia or ES2 pedicle screws must be used as part of the study protocol).

Statistical Methodology	
All continuous data will be summarized using continuous descriptive statistics: number of subjects with responses (n), mean, standard deviation, median, minimum, and maximum. Changes from baseline, where appropriate, will be calculated as the follow-up measure minus the baseline measure, where baseline is defined as the last measure prior to the AccuLIF spinal system surgical procedure.
 
All categorical data will be summarized using counts and percentages. Denominators for percentages will be the number of subjects in the respective patient population with nonmissing data.
 
For the primary endpoint of an increase of 3 degrees or more of segmental lordosis, a one-sided analysis (<math>\alpha=0.05</math>) will be used to assess significance. A one-sample t-test will be employed. Although the primary analysis will be at 24 months, similar analyses will be performed at each visit. Both the change from baseline and the results at each visit will be summarized.
 
For all other radiographic parameters, the change from baseline will be analyzed at each visit using two-sided, one-sample t-tests (<math>\alpha=0.05</math>) comparing the change from baseline to 0.
 
Secondary and exploratory endpoints will be analyzed where appropriate. Where changes from baseline can be calculated for numerical data, statistical analyses will be performed. Analyses will follow the two-sided approach taken for the primary analyses. Data that is ordinal in nature, such as the changes in clinical outcomes, may be analyzed using Wilcoxon signed rank tests, comparing baseline measures to follow-up measures. All analyses will be two-sided and evaluated at an alpha level of 0.05.

CONFIDENTIAL

This material is the property of Stryker Spine. Do not disclose or use except as authorized in writing by Stryker.  
Page 12

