## Evaluation Schedule

Evaluation	Preop	Peri-op	6 weeks ( $\pm$ 2 wks)	3 months ( $\pm$ 1 mo)	6 months ( $\pm$ 1 mo)	1 year ( $\pm$ 2 mos)	2 years ( $\pm$ 2 mos)
Inclusion/ Exclusion	X						
Demographics & Medical History	X						
Preoperative Functional Evaluation	X						
Surgical Details		X					
SF-12	X		X	X	X	X	X
Post- operative Functional Evaluation			X	X	X	X	X
VAS (back and leg)	X		X	X	X	X	X
ODI	X		X	X	X	X	X
AP/Lateral	X		X	X	X	X	X
Flexion/Extension	X					X	X
Long standing Lateral	X					X	
MRI	X						
CT (fusion analysis)						X	X*

\* Month 24 CTs are only expected for subjects that did not have a successful fusion at Month 12. All Month 24 CT collected will be analyzed.

CONFIDENTIAL

This material is the property of Stryker Spine. Do not disclose or use except as authorized in writing by Stryker.  
 Page 13

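### The plan hypothesises that regional and global sagittal balance is maintained, but tests mean change only against 0, which cannot support maintenance when the true change is null or small

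*Combined protocol and SAP*

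**What the plan says.** The Hypothesis row of the synopsis, repeated in section 2.1, expects the device to restore disc height and to "improve segmental lordosis and maintain regional and global sagittal balance post operatively". Section 1.1 also gives maintaining sagittal balance as part of the study's purpose. Regional lordosis (T12-S1, degrees) and sagittal balance (C7-S1, mm) are both listed as primary radiographic parameters in the synopsis and in sections 2.1 and 9.1.1.

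Section 9.1.3 sets the analysis for every radiographic parameter other than segmental lordosis: "the change from baseline will be analyzed at each visit using two-sided, one-sample t-tests (alpha=0.05) comparing the change from baseline to 0". The Statistical Methodology row of the synopsis has the same rule: "For all other radiographic parameters, the change from baseline will be analyzed at each visit using two-sided, one-sample t-tests".

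On timing, section 9.1.1 says of the whole primary parameter set: "The primary objective will be evaluated at 12 months post-operatively". In the Evaluation Schedule, the row "Long standing Lateral" is marked before surgery and at 1 year only, and section 7.6 agrees.

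The formal hypothesis in section 9.1.2 concerns segmental lordosis alone; its null is "less than 3 degrees increase in segmental lordosis 12 months post-operatively". The 3-degree threshold and the sample size in section 9.4.2 also belong to segmental lordosis.

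**The concern.** Restoring or improving a measure and maintaining it are different kinds of claim. A test against 0 suits disc height, where a change is expected. For a measure expected to stay put, the same test can reject 'no mean change' but cannot confirm it. A non-significant result may mean that balance held, or only that the data were too few or too variable to show a loss.

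At stake is how the results on these two parameters are read. The study has no control group (section 6.2), and multi-center publications are planned at 6 weeks, 1 year and 2 years (section 16). Without a margin or a reading rule, a p-value above 0.05 could be reported as maintenance, and fewer evaluable films would make that p-value easier to obtain.

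**Working it through.** **Inputs from the documents.** Two-sided one-sample t-test, alpha 0.05, null mean change 0 (section 9.1.3). For segmental lordosis: true change 5 degrees, null 3 degrees, SD up to 6 degrees, 90% power, 79 evaluable, up to 20% dropout, 100 enrolled (section 9.4.2). No SD, margin or expected change is given for T12-S1 or C7-S1.

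**The plan's own figure.** With difference 5 − 3 = 2, SD 6 and one-sided alpha 0.05, the noncentral t gives n = 79 (power 90.2%). Dropout: 79 / (1 − 0.20) = 98.75, so 99, stated as 100. The sample size reproduces and is not in question.

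**When the test against 0 is significant.** The observed mean change must exceed t(0.975, n−1) / √n observed SDs. At n = 79 this is 1.991 / 8.888 = 0.224 SD.

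**How often a true loss is non-significant.** For a true loss of δ SDs, the test statistic is noncentral t with n − 1 degrees of freedom and noncentrality δ√n. At n = 79 the noncentrality is 0.2 × 8.888 = 1.78 or 0.3 × 8.888 = 2.67.

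| Evaluable n | Significance threshold (SD) | Non-significant, true loss 0.2 SD | Non-significant, true loss 0.3 SD |
|---|---|---|---|
| 60 (assumed further loss of films) | 0.258 | 67% | 37% |
| 79 (plan) | 0.224 | 58% | 25% |
| 100 (no loss) | 0.198 | 49% | 16% |

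**Two examples at n = 79, with assumed values.**
- Observed −2.0 degrees, SD 10: SE = 10 / 8.888 = 1.125, t = −1.78, p = 0.08, 95% CI −4.2 to +0.2. The result is non-significant, yet a mean loss of 4 degrees is not excluded.
- Observed −1.5 degrees, SD 6: SE = 0.675, t = −2.22, p = 0.03, 95% CI −2.8 to −0.2. The result is significant, yet the interval lies wholly inside an illustrative 3-degree margin.

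**Whether the exploratory percentage fills the gap.** Sections 2.3 and 9.1.6 count subjects with more than 3 degrees of lordosis gain and no negative change on both balance measures. There is no tolerance and no target percentage. Suppose changes on the two balance measures are bivariate normal with mean 0 and correlation ρ. The chance that neither is negative is 1/4 + arcsin(ρ) / 2π, which is 25% at ρ = 0 and 37% at ρ = 0.7, before the 3-degree condition is applied. A low percentage is therefore compatible with no mean change.

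**What a margin rule would need.** Assume a true change of 0 and n = 79, and require the bound on the worsening side to exclude the margin.

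| Bound used | Margin for 80% / 90% power | Power for an illustrative 3-degree margin at SD 6, 9, 12, 15 |
|---|---|---|
| Two-sided 95% CI (one-sided 0.025) | 0.32 / 0.37 SD | 99%, 83%, 59%, 42% |
| One-sided 0.05, as in the primary test | 0.28 / 0.33 SD | 99.7%, 90%, 71%, 55% |

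**The case against.** The strongest reply is that the test is not empty and that maintenance is not the formal hypothesis. A significant worsening would count against maintenance, and a significant improvement would exclude mean worsening. Nothing in the documents says that non-significance will be read as maintenance. The planned n, mean and SD (section 9.4.1) let any reader form an interval. All of this stands, and it confines the gap to null or small changes. It does not close the gap, because maintenance predicts exactly a null or small change.

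It is also true that nothing shows 0.2 SD to be clinically important, that 79 already allows for the 20% dropout, and that n = 60 is a further assumption. The percentages describe what the test can detect; they do not show a loss that matters.

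Reading 'regional' balance as T12-S1 lordosis is an inference, since no parameter carries the name regional sagittal balance. Sections 2.3 and 9.1.6 support it by pairing regional lordosis with global sagittal balance.

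A reader might infer that C7-S1 lacks a film at its primary analysis, because the synopsis says "Although the primary analysis will be at 24 months, similar analyses will be performed at each visit" while section 7.7 lists for 24 months only "AP/Lateral and Flexion/Extension radiographs will be taken". The documents do not support this. The 24-month sentence sits in the paragraph on the segmental lordosis test; the next paragraph, on the other parameters, names no primary visit. Section 9.1.1 puts the whole parameter set at 12 months, when the long standing lateral film is scheduled. Nor do the documents say which film C7-S1 is read from. The conflict between 12 months in section 9.1.3 and 24 months in the synopsis is real, but it concerns the segmental lordosis test and is a separate point.

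Section 9.1.6 mentions a formal statistical analysis plan that is not among the documents. Its stated content is the literature sources, but it could also hold a maintenance rule.

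**Conclusion.** The point holds within those limits. The plan states a maintenance hypothesis for two listed primary parameters and offers, at cohort level, only a test against 0, with no margin and no reading rule. At n = 79 that test leaves a true mean loss of 0.2 SD non-significant 58% of the time and of 0.3 SD 25%. These figures assume only a t-test on approximately normal changes. Every SD for T12-S1, the 3-degree margin and n = 60 are assumptions used for illustration.

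It would go too far to say that no possible result bears on maintenance, or that the trial's primary conclusion is at risk. The segmental lordosis hypothesis, its success criterion and the 79/100 sample size are untouched. The change should be made, but it concerns the reading of two parameters and not the design.

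**What to change.** In section 9.1.3 and the matching synopsis text, for regional lordosis and C7-S1 balance at 12 months:

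1. Report the mean change with a two-sided 95% confidence interval.
2. State which direction is worsening for each measure.
3. State that a non-significant test against 0 will not be read as maintenance.
4. Conclude maintenance only if the bound on the worsening side excludes a margin that the sponsor justifies before analysis. State the confidence level; a one-sided 0.05 level, as in the primary test, would be less strict.

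If no margin can be justified, remove 'maintain' from the hypothesis and report the estimates with intervals. If the separate analysis plan mentioned in section 9.1.6 already holds such a rule, a cross-reference is enough.

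The cost is a short amendment, which section 14 sends to the EC/IRB, and two margins to justify. No visits, films or subjects are added. The downside is a possibly inconclusive result if the SD of change is large: under the 95% rule at n = 79, a margin below about 0.32 SD has less than 80% power even when nothing has changed.
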